In the D8488C00001 study, 18-Fluoro-deoxyglucose positron emission tomography (FDG-PET) scans may be used as a method for identifying new lesions, according with the following algorithm: New lesions will be recorded where there is positive 18-Fluoro-deoxyglucose uptake³ not present on baseline FDG-PET scan or in a location corresponding to a new lesion on CT/MRI at the same follow-up visit. If there is no baseline FDG-PET scan available, and no evidence of new lesions on CT/MRI scans then follow-up CT/MRI assessments should be continued, scheduled as per protocol or clinical indicated, in order to confirm new lesions.

TUMOUR RESPONSE EVALUATION

Schedule of evaluation

³ A positive FDG-PET scan lesion should be reported only when an uptake greater than twice that of the surrounding tissue is observed.

Baseline assessments should encompass all areas of known predilection for metastases in the disease under evaluation and should additionally investigate areas that may be involved based on signs and symptoms of individual patients and should be performed within the 28 days prior to randomisation and ideally as close as possible before the start of study treatment (see the Schedule of Assessments [Table 5] in the main body of the protocol). Follow-up assessments will be performed every 8 weeks (± 1 week), relative to first dose of investigational product(s) until confirmed objective disease progression as defined by RECIST 1.1 (irrespective of the reason for stopping treatment and/or subsequent therapy).

Any other sites at which new disease is suspected should also be adequately imaged at follow-up.

If an unscheduled assessment was performed and the patient has not progressed, every attempt should be made to perform the subsequent assessments at their scheduled visits. This schedule is to be followed in order to minimise any unintentional bias caused by some patients being assessed at a different frequency than other patients.

Target lesions

Documentation of target lesions

A maximum of 5 measurable lesions, with a maximum of 2 lesions per organ (including lymph nodes), representative of all lesions involved should be identified as TL at baseline. Target lesions should be selected on the basis of their size (longest diameter for non-nodal lesions or short axis for nodal lesions), but in addition should be those that lend themselves to reproducible repeated measurements. It may be the case that, on occasion, the largest lesion does not lend itself to reproducible measurement in which circumstance the next largest lesion, which can be measured reproducibly, should be selected.

The site and location of each TL should be documented as well as the longest diameter for non-nodal lesions (or short axis for lymph nodes). All measurements should be recorded in millimetres. At baseline the sum of the diameters for all TL will be calculated and reported as the baseline sum of diameters. At follow-up visits the sum of diameters for all TL will be calculated and reported as the follow-up sum of diameters.

Special cases:

For TL measurable in 2 or 3 dimensions, always report the longest diameter. For pathological lymph nodes measurable in 2 or 3 dimensions, always report the short axis.

If the CT/MRI slice thickness used is >5 mm, the minimum size of measurable disease at baseline should be twice the slice thickness of the baseline scan.

If a lesion has completely disappeared, the longest diameter should be recorded as 0 mm.

If a TL splits into 2 or more parts, then record the sum of the diameters of those parts.

If 2 or more TLs merge then the sum of the diameters of the combined lesion should be recorded for 1 of the lesions and 0 mm recorded for the other lesion(s).

If a TL is believed to be present and is faintly seen but too small to measure, a default value of 5 mm should be assigned. If an accurate measure can be given, this should be recorded, even if it is below 5 mm.

If a TL cannot be measured accurately due to it being too large, provide an estimate of the size of the lesion.

When a TL has had any intervention eg, radiotherapy, embolisation, surgery, during the study, the size of the TL should still be provided where possible.

Evaluation of target lesions

This section provides the definitions of the criteria used to determine objective tumour visit response for TL (see Table 21).

Table 21 Evaluation of target lesions

Complete Response (CR)	Disappearance of all TLs since baseline. Any pathological lymph nodes selected as TLs must have a reduction in short axis to <10 mm.
Partial Response (PR)	At least a 30% decrease in the sum of the diameters of TL, taking as reference the baseline sum of diameters
Stable Disease (SD)	Neither sufficient shrinkage to qualify for PR nor sufficient increase to qualify for PD
Progression of disease (PD)	At least a 20% increase in the sum of diameters of TLs, taking as reference the smallest sum on study (this includes the baseline sum if that is the smallest on study). In addition to the relative increase of 20%, the sum must also demonstrate an absolute increase of at least 5 mm.
Not Evaluable (NE)	Only relevant if any of the TLs were not assessed or not evaluable or had a lesion intervention at this visit. Note: If the sum of diameters meets the progressive disease criteria, progressive disease overrides not evaluable as a TL response

CR Complete response; PR Partial response; PD Progression of disease; NE Not evaluable; SD Stable disease; TL Target lesion.

Non-target lesions

Evaluation of non-target lesions

All other lesions (or sites of disease) not recorded as TL should be identified as NTL at baseline. Measurements are not required for these lesions, but their status should be followed at subsequent visits. At each visit an overall assessment of the NTL response should be recorded by the Investigator. This section provides the definitions of the criteria used to determine and record overall response for NTL at the investigational site at each visit (see [Table 22](#)).

Table 22 Evaluation of non-target lesions

Complete response (CR)	Disappearance of all NTLs since baseline. All lymph nodes must be non-pathological in size (<10 mm short axis).
Non CR/Non PD	Persistence of 1 or more NTL.
Progression of disease (PD)	Unequivocal progression of existing NTLs. Unequivocal progression may be due to an important progression in 1 lesion only or in several lesions. In all cases the progression MUST be clinically significant for the physician to consider changing (or stopping) therapy.
Not evaluable (NE)	Only relevant when 1 or some of the NTLs were not assessed and, in the Investigator's opinion, they are not able to provide an evaluable overall NTL assessment at this visit.

CR Complete response; PR Partial response; PD Progression of disease; NE Not evaluable; NTL Non-target lesion.

To achieve 'unequivocal progression' on the basis of NTLs, there must be an overall level of substantial worsening in non-target disease such that, even in presence of stable disease or partial response in TLs, the overall tumour burden has increased sufficiently to merit discontinuation of therapy. A modest 'increase' in the size of 1 or more NTLs is usually not sufficient to qualify for unequivocal progression status.

New lesions

Details of any new lesions will also be recorded with the date of assessment. The presence of one or more new lesions is assessed as progression.

A lesion identified at a follow-up assessment in an anatomical location that was not scanned at baseline is considered a new lesion and will indicate disease progression.

The finding of a new lesion should be unequivocal: ie, not attributable to differences in scanning technique, change in imaging modality or findings thought to represent something other than tumour.

If a new lesion is equivocal, for example because of its small size, the treatment and tumour assessments should be continued until the new lesion has been confirmed. If repeat scans confirm there is a new lesion, then the progression date should be declared using the date of the initial scan.

Symptomatic deterioration

Symptomatic deterioration is not a descriptor of an objective response: it may be a reason for stopping study therapy.

Patients with ‘symptomatic deterioration’ requiring discontinuation of treatment without objective evidence of disease progression at that time should continue to undergo tumour assessments where possible until objective disease progression is observed.

Evaluation of overall visit response

The overall visit response will be derived using the algorithm shown in Table 23.

Target lesions	Non-target lesions	New lesions	Overall response
CR	CR	No	CR
CR	N/A	No	CR
CR	Non CR/Non PD	No	PR
CR	NE	No	PR
PR	Non PD or NE	No	PR
SD	Non PD or NE	No	SD
NE	Non PD or NE	No	NE
PD	Any	Yes or No	PD
Any	PD	Yes or No	PD
Any	Any	Yes	PD

CR Complete Response, PR Partial Response, SD Stable Disease, PD Progressive Disease, NE not evaluable, N/A not applicable (only if relevant if there were no NTL at baseline)

CONFIRMATION OF PROGRESSION

While disease progression may require confirmation, it is not mandated in this study. Confirmation will be subject to the investigator's discretion (eg. if investigator is not sure of progression at initial assessment). The confirmatory scan should occur preferably at the next scheduled visit and no earlier than 4 weeks after the initial assessment of progression of disease (PD) in the absence of clinical deterioration.

If a patient discontinues treatment (and/or receives a subsequent cancer therapy) prior to progression then the patient should still continue to be followed until objective disease progression.

CONFIRMATION OF RESPONSE

In Study D8488C00001, imaging for confirmation of response (CR or PR) should be performed at the next scheduled RECIST assessment, 8 weeks (certainly no less than 4 weeks) following the date the criteria for response were first met.

CENTRAL REVIEW

The Contract Research Organisation appointed by AstraZeneca to perform the independent central review for the primary analysis of this study will provide specification for radiological imaging protocols in standard acquisition guidelines documentation.

REFERENCES

Eisenhauer et al 2009

Appendix G Hypertension Medication

The following anti-hypertensive medications have been provided as a guide and those used in this study will depend upon local practice.

Note: Agents in bold characters are suggested as optimal choices to avoid or minimize potential drug-interactions with cediranib through cytochrome P450 (CYP450)

Table 24 Dihydropyridine calcium-channel blockers

Agent	Initial dose	Intermediate dose	Maximum dose	Hepatic metabolism?
Nifedipine XL	30 mg po qd	60 mg po qd	90 mg po qd	CYP 3A4 substrate
Amlodipine	2.5 mg po qd	5 mg po qd	10 mg po qd	CYP 3A4 substrate
Felodipine	2.5 mg po qd		10 mg po qd	CYP 3A4 substrate + inhibitor

Abbreviations: po oral; qd once daily

Table 25 Selective beta-blockers

Agent	Initial dose	Intermediate dose	Maximum dose	Hepatic metabolism?
Metoprolol	25 mg po bd	50 mg po bd	100 mg po bd	CYP2D6 substrate
Atenolol	25 mg po qd	50 mg po qd	100 mg po qd	No
Acebutolol	100 mg po bd	200-300 mg po bd	400 mg po bid	Yes (CYP450 questionable)
Bisoprolol	2.5 mg po qd	5-10 mg po bd	20 mg po qd	Yes (CYP450 questionable)

Abbreviations: bd twice daily; po oral; qd once daily

Table 26 Angiotensin Converting Enzyme Inhibitors (ACEIs)

Agent	Initial dose	Intermediate dose	Maximum dose	Hepatic metabolism?
Captopril	12.5 po tid	25 mg po tid	50 mg po tid	CYP 2D6 substrate
Enalapril	5 mg po qd	10-20 mg po qd	40 mg po qd	CYP 3A4 substrate
Ramipril	2.5 mg po qd	5 mg po qd	10 mg po qd	Yes (CYP450 questionable)
Lisinopril	5 mg po qd	10-20 mg po qd	40 mg po qd	No
Fosinopril Rarely used:	10 mg po qd	20 mg po qd	40 mg po qd	Yes (CYP450 questionable)
Perindopril	4 mg po qd	none	8 mg po qd	Yes but not per CYP450
Quinapril	10 mg po qd	20 mg po qd	40 mg po qd	No

Abbreviations: po oral; tid three times daily; qd once daily

Table 27 Angiotensin II Receptors Blockers (ARBs)

Agent	Initial dose	Intermediate dose	Maximum dose	Hepatic metabolism?
Losartan	25 mg po qd	50 mg po qd	100 mg po qd	CYP3A4 substrate
Candesartan	4 mg po qd	8-16 mg po qd	32 mg po qd	CYP2C9 substrate
Irbesartan	75 mg po qd	150 mg po qd	300 mg po qd	CYP2C9 substrate
Telmisartan	40 mg po qd	none	80 mg po qd	Yes but not per CYP450
Valsartan	80 mg po qd	none	160 mg po qd	Yes but not per CYP450

Abbreviations: po oral; qd once daily

Table 28 Alpha and beta-blocker

Agent	Initial dose	Intermediate dose	Maximum dose	Hepatic metabolism?
Labetolol	100 mg po bid	200 mg po bd	400 mg po bd	CYP 2D6 substrate and inhibitor

Abbreviations: bd twice daily; po oral

Clinical Study Protocol
Drug Substance cediranib (AZD2171) plus olaparib (AZD2281)
Study Code D8488C00001
Edition Number 5.0
Date 15 Jan 2019

CC
I

Appendix I List of CYP3A4 inhibitors and inducers

GUIDANCE REGARDING POTENTIAL INTERACTIONS WITH CONCOMITANT MEDICATIONS

Note. While this is not an exhaustive list, it covers the known potent inhibitors and inducers, which have most often previously been reported to be associated with clinically significant drug interactions. Please contact the Medical Monitor or AstraZeneca physician if further clarification is required. For a more detailed list of CYP3A4 inhibitors/inducers, please visit FDA website:

<http://www.fda.gov/Drugs/DevelopmentApprovalProcess/DevelopmentResources/DrugInteractionsLabeling/ucm093664.htm#4>

INTERACTIONS WITH P450:

Olaparib is substrate of CYP3A4. Therefore, CYP3A4 inhibitors and inducers will affect olaparib's exposure. Cediranib is not substrate of CYP3A4, but it is substrate of UGT and Pgp. Some CYP3A4 inhibitors and inducers also inhibit or induce UGT/Pgp.

POTENT INHIBITORS OF CYP3A4:

The following inhibitors of CYP3A4 must not be used during this study:

Table 30 Potent inhibitors of CYP3A4

Drug	Minimum washout period prior to starting IP
Ketoconazole; Itraconazole; Indinavir; Saquinavir; Telithromycin; Nelfinavir; Clarithromycin; Ritonavir; Cobicistat; Indinavir; Saquinavir; Nelfinavir; Boceprevir; Telaprevir and Clarithromycin	2 Weeks

Moderate CYP3A inhibitors (eg. ciprofloxacin, erythromycin, diltiazem, fluconazole, verapamil) should be avoided with at least 1 week washout period.

INDUCERS OF CYP3A4:

In addition, to avoid potential reductions in exposure due to drug interactions, the following CYP3A4 inducers should be avoided:

Table 31 **Potent inducers of CYP3A/4**

Drug	Minimum washout period prior to starting IP
Carbamazepine; Modafinil; Nevirapine; Phenytoin; Rifabutin; Rifampicin; Rifapentin; St John's Wort (Hypericum perforatum); Bosentan; Efavirenz; Modafinil.	4 Weeks
Phenobarbitone; Enzalutamide	5 Weeks

After recruitment, if the use of any potent inducers or inhibitors of CYP3A4 are considered necessary for the patient's safety and welfare, the investigator must contact the AstraZeneca Study Physician. A decision to allow the patient to continue in the study will be made on a case-by-case basis.

NATURAL / HERBAL PRODUCTS:

The use of any natural/herbal products or other "folk remedies" should be discouraged but use of these products, as well as use of all vitamins, nutritional supplements and all other concomitant medications must be recorded in the appropriate eCRF.

Appendix J Acceptable Birth Control Methods

OLAPARIB AND CEDIRANIB ARE REGARDED AS COMPOUNDS WITH FOETAL RISK

- Women of childbearing potential and their partners, who are sexually active, must agree to the use of TWO highly effective forms of contraception in combination [as listed below], throughout the period of taking study treatment and for at least 6 weeks after last dose of study drug(s), or they must totally/truly abstain from any form of sexual intercourse (see below).

ACCEPTABLE NON-HORMONAL BIRTH CONTROL METHODS INCLUDE:

- Total sexual abstinence. Abstinence must continue for the total duration of study treatment and for at least 1 month after the last dose. Periodic abstinence (eg, calendar ovulation, symptothermal post ovulation methods) and withdrawal are not acceptable methods of contraception.
- Vasectomised sexual partner PLUS male condom. With participant assurance that partner received post-vasectomy confirmation of azoospermia.
- Tubal occlusion PLUS male condom
- IUD PLUS male condom, provided coils are copper-banded

ACCEPTABLE HORMONAL METHODS:

- Normal and low dose combined oral pills PLUS male condom
- Cerazette (desogestrel) PLUS male condom. Cerazette is currently the only highly efficacious progesterone based pill.
- Hormonal shot or injection (eg., Depo-Provera) PLUS male condom
- Etonogestrel implants (eg, Implanon, Norplant) PLUS male condom
- Norelgestromin / EE transdermal system PLUS male condom
- Intrauterine system [IUS] device (eg, levonorgestrel releasing IUS -Mirena[®]) PLUS male condom
- Intravaginal device (eg, EE and etonogestrel) PLUS male condom.

Clinical Study Protocol
Drug Substance cediranib (AZD2171) plus olaparib (AZD2281)
Study Code D8488C00001
Edition Number 5.0
Date 15 Jan 2019

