3.8 Restrictions

Patients should not donate blood while participating in this study and for at least 3 months following the last dose of IPs.

Absorption of oral contraceptives can be impaired in case of GI symptoms such as diarrhea >24 hours or vomiting. In addition, the possibility that cediranib may induce GI CYP3A and uridine diphosphate glucuronosyltransferase (UGT) enzymes cannot be excluded and the efficacy of hormonal contraceptives may be reduced if co administered with cediranib.

Therefore, women of child-bearing potential must agree to use two highly effective forms of contraception (see Appendix J) during study treatment and for at least 6 weeks after discontinuation of study treatment and to perform pregnancy tests as required (see Sections 5.2.5.1, 6.6.1). Should a woman become pregnant or suspect she is pregnant during the study conduct, she should inform her treating physician immediately. Breast-feeding is contraindicated whilst receiving IPs.

Restrictions related to pregnancy are provided in Section 6.6. Restrictions related to concomitant medications (including medications metabolized via CYP3A4/5 or P glycoprotein (PgP)/UGT; anticoagulant therapy; anti-emetics/anti-diarrheal therapies; palliative RT and administration of other anti-cancer agents) are described in Section 7.7 and Appendix I.

Patients may not use any complementary or alternative medicines including natural herbal products or folk remedies as they may interfere with the effectiveness of the IPs.

It is prohibited to consume grapefruit juice while on olaparib therapy.

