6.6.1 Maternal exposure

Women of childbearing potential must use any two highly effective forms of contraceptive methods in combination to avoid becoming pregnant while receiving IPs and for at least 6 weeks following the last dose of study treatments (cediranib + olaparib). The efficacy of hormonal contraceptives may be reduced if co-administered with cediranib (see Section 3.8); therefore, an additional non-hormonal contraceptive method should be used during treatment (see Appendix J) and pregnancy tests performed as required per SOA See Table 5). Should a pregnancy still occur, the IPs should be discontinued immediately and the pregnancy reported to AstraZeneca.

Pregnancy itself is not regarded as an adverse event unless there is a suspicion that the IPs under study may have interfered with the effectiveness of a contraceptive medication. Congenital abnormalities/birth defects and spontaneous miscarriages should be reported and handled as SAEs. Elective abortions without complications should not be handled as AEs. The outcome of all pregnancies (spontaneous miscarriage, elective termination, ectopic pregnancy, normal birth or congenital abnormality) occurring from the date of the first dose of study medication until 6 weeks after the last dose of study medication should be followed up and documented even if the patient was discontinued from the study.

If any pregnancy occurs in the course of the study, then the Investigator or other site personnel informs the appropriate AstraZeneca representatives within 1 day ie, immediately but no later than 24 hours of when he or she becomes aware of it.

The designated AstraZeneca representative works with the Investigator to ensure that all relevant information is provided to the AstraZeneca Patient Safety data entry site within 1 or 5 calendar days for SAEs (see Section 6.4) and within 30 days for all other pregnancies.

The same timelines apply when outcome information is available.

The PREGREP module in the eCRF is used to report the pregnancy and the PREGOUT is used to report the outcome of the pregnancy.

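### Appendix J lets abstinence end 1 month after the last dose, 11 to 14 days short of the 6 weeks the protocol uses everywhere else for avoiding pregnancy

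*Protocol*

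**What the plan says.** Four places in the current protocol (Edition 5.0) bear on how long pregnancy must be avoided after treatment stops.

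- **Appendix J, lead sentence.** Sexually active women of childbearing potential and their partners must use two highly effective methods "throughout the period of taking study treatment and for at least 6 weeks after last dose of study drug(s), or they must totally/truly abstain". For the abstinence option the sentence sends the reader to the list below it.
- **Appendix J, abstinence bullet.** This is the text the lead sentence points to: "Abstinence must continue for the total duration of study treatment and for at least 1 month after the last dose".
- **Section 3.8 (Restrictions).** Women of childbearing potential must agree to two highly effective methods "during study treatment and for at least 6 weeks after discontinuation of study treatment". The section refers to Appendix J for the methods.
- **Section 6.6.1 (Maternal exposure).** Two methods are required while on treatment and "for at least 6 weeks following the last dose of study treatments". Pregnancies occurring from the first dose "until 6 weeks after the last dose of study medication should be followed up and documented".

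**The concern.** The period of foetal risk after the last dose is a property of the drugs. It does not depend on how a woman avoids pregnancy. A shorter minimum for one accepted method therefore needs a reason, and none is given.

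Appendix J is the only place that says how long abstinence must last, and abstinence is the only listed method with a duration of its own. A site or patient looking up the rule would naturally apply that bullet. Following it alone, a woman could resume intercourse while still inside the 6-week period that Section 6.6.1 treats as relevant for pregnancy follow-up.

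The uncovered days also fall at about or after the 30-day safety follow-up visit. For patients treated beyond the Final Protocol Visit, Section 4.5 monitors pregnancies for only 30 days after the last dose. A conception after day 30 but before day 42 could escape routine monitoring in those women.

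**Working it through.** The check is calendar arithmetic and a comparison of texts. No sample size, power or error rate is involved.

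**Inputs**

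| Source | What it governs | Minimum after treatment |
|---|---|---|
| Appendix J, lead sentence | two contraceptive methods | 6 weeks |
| Section 3.8 | two contraceptive methods | 6 weeks |
| Section 6.6.1 | two contraceptive methods | 6 weeks |
| Section 6.6.1 | pregnancies to be followed up | 6 weeks |
| Appendix J, bullet | abstinence | 1 month |

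**Gap** = 6 weeks in days minus 1 calendar month in days, with 6 × 7 = 42 days.

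| Length of month (days) | Gap (days) |
|---|---|
| 28 | 42 − 28 = 14 |
| 29 | 42 − 29 = 13 |
| 30 | 42 − 30 = 12 |
| 31 | 42 − 31 = 11 |

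The shortfall is 11 to 14 days. With the bullet set to 6 weeks it is 42 − 42 = 0.

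**Is the difference deliberate?** No passage gives a reason for a shorter abstinence period or states a 6-week minimum for abstinence elsewhere. As background only, the Version 3.0 entry in the Version History says the Appendix J requirement was raised from 4 weeks, which applied to olaparib, to 6 weeks because of the cediranib Investigator Brochure. A bullet left unedited at that point would explain the 1-month figure. That is an inference, and the finding does not depend on it, because the conflict is between passages of current text.

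**How many patients?** Section 1.4 plans approximately 60. Inclusion criterion 15 counts as postmenopausal, among others, women aged 60 or over and women with bilateral oophorectomy or hysterectomy. Women of childbearing potential can still enter with a negative pregnancy test, and Section 5.2.5.1 schedules 4-weekly tests for them. The documents do not say how many there will be or how many will rely on abstinence.

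**The case against.** The strongest reply is that the 6-week rule never slackens. Wherever it appears, the 6 weeks is worded for two-method contraception. Sections 3.8 and 6.6.1 do not mention abstinence, and in the Appendix J lead sentence abstinence is an alternative with no period of its own. A woman who stops abstaining at day 32 becomes sexually active, and on this reading she falls under the two-method rule until day 42. One month is also stated as a floor, so abstaining for 6 weeks satisfies both texts. The 11 to 14 days would then be a difference in wording and not a permitted gap.

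That reading is available, and it limits the claim: the protocol does not clearly allow unprotected intercourse before week 6. It does not remove the inconsistency. The reader has to combine three places to reach the safe answer, while the bullet that specifically governs abstinence gives a shorter one.

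Two further points stand. Few patients, possibly none, will be affected. What patients are actually told cannot be checked, because patient-facing text is not in the copy reviewed. Both bear on how much weight the point deserves, not on whether the bullet should be corrected.

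**Conclusion.** The concern holds. The abstinence bullet is inconsistent with the 6-week period in its own appendix and in Sections 3.8 and 6.6.1, by 11 to 14 days depending on the length of the month. It is best described as an internal inconsistency, since nothing suggests that a shorter period was chosen on purpose.

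The judgement that few women are affected rests on the planned size of approximately 60 and the breadth of criterion 15. It is an assumption, not a figure from the documents. This is a patient-safety wording point: no endpoint, analysis set, sample size or SAP method changes. It should be corrected because the harm, if it occurred, could be serious and the instruction ought to be right for any woman it applies to. Patients may continue treatment after the data cut-off, so the wording can still matter late in the study.

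**What to change.** In the Appendix J abstinence bullet, replace the 1-month minimum after the last dose with a minimum of 6 weeks, so that it matches the lead sentence and Sections 3.8 and 6.6.1. Check the consent form and any other patient-facing material for the same figure.

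In the protocol this is a one-line correction. Whether patient-facing text also needs changing, and what that would cost, cannot be judged from the documents available.
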